9.1.1.2 Laboratory safety variables

The clinical laboratory data consist of blood analysis (including hematology and biochemistry) and urinalysis. Clinical laboratory values will be analyzed by a central laboratory. These values will be analyzed after conversion into standard international units, and international units will be used in all listings and tables.

Blood samples should be drawn in fasting conditions for:

- Hematology: red blood cell count, hematocrit, hemoglobin, white blood cell count with differential count (neutrophils, eosinophils, basophils, monocytes, and lymphocytes), platelets.
- Biochemistry:
 - Plasma/serum electrolytes: sodium, potassium, chloride, calcium,
 - Liver function: aspartate aminotransferase (AST), alanine aminotransferase (ALT), alkaline phosphatase, gamma-glutamyl transferase, total and conjugated bilirubin,
 - Renal function: creatinine, blood urea nitrogen, uric acid,
 - Metabolic panel: glucose, albumin, total proteins, total cholesterol, triglycerides,
 - Potential muscle toxicity: creatine kinase (CK), CK with MB fraction, lactate dehydrogenase,
 - Brain natriuretic peptide (BNP).

Urinalysis will include urine color, appearance, specific gravity, proteins, glucose, erythrocytes, leucocytes, ketone bodies, and pH to be assessed:

- Qualitatively: A dipstick is to be performed on a freshly voided specimen for qualitative detection using a reagent strip.
- Quantitatively: A quantitative measurement for protein, erythrocytes, and leukocytes count will be required in the event that the urine sample test is positive for any of the above parameters by urine dipstick (eg, to confirm any positive dipstick parameter by a quantitative measurement).

9.1.1.3 *Vital signs*

Vital signs include heart rate, systolic and diastolic blood pressure, respiratory rate, temperature, and oxygen saturation. Vital signs are to be assessed prior to infusion, with each infusion rate change (including the start of infusion that is considered as first infusion rate change), at the end of the infusion, and at the end of the post-infusion observation period. Collection windows are ± 15 minutes.

9.1.1.4 *Electrocardiogram variables*

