11.4.2.3 Physical examination, vital signs, and electrocardiogram

Potentially clinically significant findings observed during the on-treatment period for vital signs (including but not limited to blood pressure, heart rate, respiratory rate, etc) and ECG (QTc, PR interval, etc) will be summarized by study cohort and treatment group, as well as by dose levels among avalglucosidase alfa-treated patients. Listings of abnormal findings/values from these data as well as from PE assessment inclusive of body weight and height, as well as head circumference and Tanner stage, will be presented.

11.4.2.4 Anti-avalglucosidase alfa and anti-alglucosidase alfa antibodies, neutralizing antibodies, and other immunogenicity testing

Percentage of patients who seroconverted to avalglucosidase alfa, time to seroconversion and peak anti-avalglucosidase alfa antibody titer will be summarized using summary statistics.

Anti-avalglucosidase alfa and anti-alglucosidase alfa antibody titer values will be summarized using summary statistics at each study visit. All data will be presented in listings for each patient.

By patient listings will also display results of neutralizing antibody, circulating immune complex, anti-avalglucosidase alfa IgE antibody, serum tryptase activity, complement activation, and skin testing performed. Descriptive summaries may also be provided as appropriate.

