2.1 ANALYSIS ENDPOINTS

2.1.1 Demographic and baseline characteristics

The PAP baseline value is defined as the last non-missing value prior to first investigational medicinal product (IMP) intake, unless otherwise specified.

The ETP baseline value is defined as:

- The last non-missing value prior to first IMP intake in PAP for patients receiving avalglucosidase alfa from the beginning of this study;
- The last non-missing value prior to first IMP intake in ETP for patients switching to avalglucosidase alfa from alglucosidase alfa.

Demographic characteristics

Demographic variables are age at study entry (year), gender (Male, Female), race (American Indian or Alaska Native, Asian, Black or Africa American, Native Hawaiian or other Pacific Islander, White, Not Reported), ethnicity (Hispanic, non-Hispanic, Unknown, Not Reported).

Medical or surgical history

Medical or surgical history includes prior or existing condition in different body systems as well as prior or existing medical conditions/surgical procedures of specific interest.

Disease characteristics at baseline

Pompe disease history includes acid α -glucosidase (GAA) genotyping, CRIM (cross-reactive immunologic material) status, GAA enzyme activity, [REDACTED], [REDACTED], aspects of disability (Pompe medical history, ventilator and assistive mobility device use), age at first symptoms of Pompe disease, age at diagnosis of Pompe disease, age at first treatment with alglucosidase alfa, time from Pompe disease diagnosis to first infusion of study drug, time from first symptoms of Pompe disease to first infusion of study drug.

Pompe medical history includes:

- Cardiovascular history (evidence of cardiac involvement, current NYHA (the New York Heart Association) heart failure classification, congestive heart failure),
- Ears, nose, throat medical history (enlarged tongue, hearing loss),
- Gastrointestinal (hepatomegaly, gastroesophageal reflux),
- Respiratory history (pneumonia, tracheostomy, sleep disturbances, sleep apnea),
- Musculoskeletal history (muscle weakness in upper extremities, muscle weakness in lower extremities, scoliosis, joint contractures, and current ambulatory status, assisted walking device and wheelchair use).

Family history of Pompe disease history includes confirmed Pompe disease in other family members.

Retrospective Chart Review

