Retrospective review of available assessments prior to study entry documents clinical decline or suboptimal clinical response. It may include the following assessments:

- Respiratory function evaluation:
 - FVC (% predicted),
 - use of ventilator support.
- Motor function evaluation:
 - gross motor milestone,
 - GMFM-88 composite score,
 - Pompe-PEDI mobility,
 - QMFT,
 - GMFCS-E&R,

- other test or assessment, if any.
- Cardiac Function Evaluation:
 - Left ventricular mass (LVM) standard score (Z-score);
 - Left ventricular mass index (LVMI; g/m²);
- Other Evaluation:
 - Presence of ptosis.

The above assessments have documented (at least 2 recent and consecutive assessments prior to study entry, not less than 2 weeks apart) evidence of clinical decline or suboptimal clinical response in at least 1 of the following parameters related to Pompe disease and NOT related to intercurrent illness as assessed by the Investigator, in addition to at least 1 previous assessment prior to onset of decline:

- For patients entering Stage 1 - clinical decline in at least 1 of the following parameters: respiratory function, motor skills, and/or cardiac parameters.
- For patients entering Stage 2 - suboptimal clinical response in at least 1 of the following parameters: respiratory function, motor skills, and/or presence of ptosis.

Growth parameters at baseline

Weight (kg), height/total body length (cm), body mass index (BMI, kg/m²), head circumference (cm) and Tanner stage of sexual maturation.

Vital signs

Vital signs include systolic blood pressure, diastolic blood pressure, heart rate, respiratory rate, temperature, and oxygen saturation. The baseline values for vital signs are the last non-missing assessment prior to the first study treatment by comparing the infusion time and measurement time.

Immunogenicity status

The immunogenicity evaluation at baseline includes antibody status (positive or negative) and magnitude (titer) of the anti-drug antibodies (ADA).

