2.4.4 Analyses of safety data

In general, for PAP, the summary of safety results will be presented by study cohort and treatment arm. For the overall avalglucosidase alfa treatment period, the summary of safety results will be presented by initial planned dose levels among avalglucosidase alfa patients. For Cohort 3 alglucosidase alfa patients, the summary of safety results for ETP will be presented in separate tables.

In the PAP analysis, the safety analyses will be carried out with patients by the actual treatment received, irrespective of the treatment the patient has been randomized to. The actual treatment received is defined as:

- avalglucosidase alfa if the patient receives at least one infusion with this drug in PAP;
- alglucosidase alfa if the patient only receives alglucosidase alfa in PAP.

In the ETP analysis and/or overall evaluation of avalglucosidase alfa safety, the safety analyses will be carried out by the following 3 groups:

- AVAL/AVAL in ETP includes data in ETP among patients who received avalglucosidase alfa in PAP and ETP;
- ALGLU/AVAL in ETP includes data in ETP among patients who received alglucosidase alfa in PAP and received avalglucosidase alfa in ETP;
- AVAL/AVAL and ALGLU/AVAL in overall avalglucosidase alfa treatment period includes data in PAP and/or ETP among patients who received avalglucosidase alfa in that period.

General rules

All safety analyses will be performed on the safety population as defined in [Section 2.3.1](#), unless otherwise specified, using the following common rules:

- The safety baseline value is defined the same as the baseline definition in [Section 2.1.1](#).
- The potentially clinically significant abnormality (PCSA) values are defined as abnormal values considered medically important by the Sponsor according to predefined criteria/thresholds based on literature review and defined by the Sponsor for clinical laboratory tests, vital signs, and ECG (PCSA version dated January 2014 [[Appendix B](#)]).
 - PCSA criteria will determine which patients had at least 1 PCSA during the treatment epoch (for PAP and ETP respectively), taking into account all evaluations performed during this period, including nonscheduled or repeated evaluations.
 - The number of all such patients will be the numerator for the on-treatment PCSA percentage; the denominator will be the number of patients assessed for that given parameter in the treatment epoch by treatment group on the safety population.

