2.4.4.4 Analyses of vital sign variables

The summary statistics of all vital signs variables (central laboratory values and changes from baseline) will be calculated for each scheduled visit or study assessment (baseline, each post-baseline time point) by study cohort and treatment group.

The incidence of PCSAs (list provided in [Appendix B](#)) based on worst value at any time during the treatment-emergent adverse event period will be summarized by study cohort and treatment groups.

The PCSA analyses will be conducted for both PAP and ETP separately. Similar analyses will be conducted for the overall avalglucosidase alfa treatment period.

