Heart rate	≤ 50 bpm and decrease from baseline ≥ 20 bpm ≥ 120 bpm and increase from baseline ≥ 20 bpm	Birth/0 to 27 days old (Neonates) ≤ 90 bpm and decrease from baseline ≥ 20 bpm ≥ 190 bpm and increase from baseline ≥ 20 bpm 28 days/1 month to 23 months old (Infants) ≤ 80 bpm and decrease from baseline ≥ 20 bpm ≥ 175 bpm and increase from baseline ≥ 20 bpm 24 months/2 years to <6 years old (Children) ≤ 75 bpm and decrease from baseline ≥ 20 bpm ≥ 140 bpm and increase from baseline ≥ 20 bpm 6 to <12 years old (Children) ≤ 50 bpm and decrease from baseline ≥ 20 bpm ≥ 120 bpm and increase from baseline ≥ 20 bpm 12 to 16/18 years old (Adolescents) ≤ 50 bpm and decrease from baseline ≥ 20 bpm ≥ 120 bpm and increase from baseline ≥ 20 bpm
Systolic BP	≤ 95 mmHg and decrease from baseline ≥ 20 mmHg ≥ 160 mmHg and increase from baseline ≥ 20 mmHg	Birth/0 to 27 days old (Neonates) ≤ 60 mmHg and decrease from baseline ≥ 20 mmHg ≥ 85 mmHg and increase from baseline ≥ 20 mmHg 28 days/1 month to 23 months old (Infants) ≤ 70 mmHg and decrease from baseline ≥ 20 mmHg ≥ 98 mmHg and increase from baseline ≥ 20 mmHg 24 months/2 years to <6 years old (Children) ≤ 70 mmHg and decrease from baseline ≥ 20 mmHg ≥ 101 mmHg and increase from baseline ≥ 20 mmHg 6 to <12 years old (Children) ≤ 80 mmHg and decrease from baseline ≥ 20 mmHg ≥ 108 mmHg and increase from baseline ≥ 20 mmHg 12 to 16/18 years old (Adolescents) ≤ 90 mmHg and decrease from baseline ≥ 20 mmHg ≥ 119 mmHg and increase from baseline ≥ 20 mmHg

Diastolic BP	≤ 45 mmHg and decrease from baseline ≥ 10 mmHg ≥ 110 mmHg and increase from baseline ≥ 10 mmHg	Birth/0 to 27 days old (Neonates) ≤ 34 mmHg and decrease from baseline ≥ 10 mmHg ≥ 50 mmHg and increase from baseline ≥ 10 mmHg 28 days/1 month to 23 months old (Infants) ≤ 34 mmHg and decrease from baseline ≥ 10 mmHg ≥ 54 mmHg and increase from baseline ≥ 10 mmHg 24 months/2 years to <6 years old (Children) ≤ 34 mmHg and decrease from baseline ≥ 10 mmHg ≥ 59 mmHg and increase from baseline ≥ 10 mmHg 6 to <12 years old (Children) ≤ 48 mmHg and decrease from baseline ≥ 10 mmHg ≥ 72 mmHg and increase from baseline ≥ 10 mmHg 12 to 16/18 years old (Adolescents) ≤ 54 mmHg and decrease from baseline ≥ 10 mmHg ≥ 78 mmHg and increase from baseline ≥ 10 mmHg
--------------	---	--

Signature Page for VV-CLIN-0258347 v2.0
act14132-16-1-9-sap

Approve & eSign

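### No planned analysis compares vital signs during an infusion with that day's pre-infusion reading, so the heart-rate and blood-pressure PCSA table can omit infusion excursions and flag values present beforehand

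*SAP*

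**What the plan says.** **Reference value.** SAP 2.1.1 states: "The baseline values for vital signs are the last non-missing assessment prior to the first study treatment". SAP 2.4.4 carries this into the safety analyses: "The safety baseline value is defined the same as the baseline definition in" Section 2.1.1. For the extension (ETP), SAP 2.1.1 uses "The last non-missing value prior to first IMP intake in PAP for patients receiving avalglucosidase alfa from the beginning of this study", and for Cohort 3 switch patients "The last non-missing value prior to first IMP intake in ETP for patients switching to avalglucosidase alfa from alglucosidase alfa". Protocol 11.4.2 has the same pre-first-dose rule and leaves further detail to the SAP.

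**Measurement.** Protocol 9.1.1.3 states: "Vital signs are to be assessed prior to infusion, with each infusion rate change", and again at the end of the infusion and at the end of the observation period. The flow charts apply this to every infusion.

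**Analysis.** Under SAP 2.4.4.4, PCSA incidence "based on worst value at any time during the treatment-emergent adverse event period will be summarized by study cohort and treatment groups". In Appendix B each paediatric heart-rate and blood-pressure criterion joins a limit to a change; the upper heart-rate criteria read "bpm and increase from baseline" of at least 20 bpm. SAP 2.4.4.4 also plans summary statistics of values and changes from baseline at each time point.

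**Coverage.** Protocol 11.4.2.3 promises a summary of potentially clinically significant findings for "vital signs (including but not limited to blood pressure, heart rate, respiratory rate, etc". The vital-sign part of Appendix B has criteria for heart rate, systolic pressure and diastolic pressure only.

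**The concern.** The repeated readings at each infusion serve to show what the infusion does to the child. That effect is the difference between a reading during or after the infusion and the reading just before it. The SAP instead subtracts a value that may be weeks or years old. When that value differs from the day's pre-infusion value, the change condition no longer measures the infusion effect, and the error can go either way.

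Vital signs belong to the primary safety endpoint, and Protocol Section 4 names infusion reactions and acute cardiorespiratory failure from fluid overload as risks. AE reporting is not a complete backstop. Under Protocol 10.4.2 a vital-sign abnormality becomes an AE only if it is symptomatic, needs treatment or consultation, leads to stopping or changing the dose, is serious, or is an AESI (Germany adds investigator-judged clinical significance). Both IAR definitions in SAP 2.1.4 start from a reported AE. An unreported excursion in one patient would have to show up in the PCSA table.

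**Working it through.** **Inputs.** From Appendix B, age 6 to <12 years: heart rate (HR) ≥120 bpm with a rise ≥20, or ≤50 with a fall ≥20; systolic pressure (SBP) ≥108 mmHg with a rise ≥20, or ≤80 with a fall ≥20. The upper HR limits in the younger bands are 175 (28 days to 23 months) and 140 (2 to <6 years). All individual readings below are assumed, because the documents give no vital-sign distributions.

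**Infusions without a same-day reference.** These counts are for every-other-week dosing with avalglucosidase alfa from the start.
- Primary period: 13 infusions. Only the first has a same-day reference, leaving 13 − 1 = 12.
- To Week 145: 13 + 60 = 73 infusions, leaving 72.

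**The rule.** With limit L and reference B, a high HR reading is flagged when it is at least max(L, B + 20). A low SBP reading is flagged when it is at most min(L, B − 20). The fixed reference raises the HR flag point above L once B exceeds L − 20, which is 155, 120 and 100 bpm for the three limits (175, 140, 120).

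**Excursions left out (child aged 8 throughout, so the age band does not matter).**

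| Sign | Day 1 | Before infusion | During | Change from Day 1 | Flag now | Same-day change | Flag same-day |
|---|---|---|---|---|---|---|---|
| HR | 115 | 85 | 130 | 130 − 115 = +15 | No | 130 − 85 = +45 | Yes (130 ≥ 120) |
| SBP | 95 | 110 | 78 | 78 − 95 = −17 | No | 78 − 110 = −32 | Yes (78 ≤ 80) |

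**Sensitivity to Day 1 HR (age 8, pre-infusion 85).** With the fixed reference the flag point is 120 for Day 1 values of 85 or 95, then 125, 135 and 145 for Day 1 values of 105, 115 and 125. With the same-day reference it is max(120, 85 + 20) = 120 throughout.

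**A value present beforehand.** Take Day 1 SBP 88 and a pre-infusion SBP of 108 at age 6 to <12. Then 108 − 88 = 20 and 108 ≥ 108, so both conditions are met with no infusion change.

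**Limits of the same-day comparison.**
- At age 8, a rise from 85 to 115 is flagged by neither reference, because 115 < 120.
- If the same-day value *replaced* the fixed one, some current flags would be lost. With Day 1 HR 90, pre-infusion 110 and infusion 125, the change is +35 now (flagged) but 125 − 110 = +15 after replacement (not flagged).

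**Length of follow-up.** The SAP plans 25 + 120 = 145 weeks (145 × 7 / 365.25 = 2.8 years); the protocol plans 25 + 120 + 226 = 371 weeks (7.1 years). A child entering at 20 months (1.67 years) is about 4.4 years old at Week 145 and still in the 2 to <6 band. With Day 1 HR 125, the fixed flag point is max(140, 145) = 145, against 140 with a same-day value of 120 or less: a gap of 5 bpm.

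**The case against.** The strongest reply is that PCSA tables are not how this plan detects infusion reactions. IARs have a protocol and an algorithm definition (SAP 2.1.4) and are tabulated by onset relative to the end of infusion (SAP 2.4.4.1). Their signs and symptoms are entered as separate AEs (Protocol 10.4.2), and pre-infusion vital signs are among the details to be considered for collection (Protocol 10.4.4). The fixed baseline also agrees with Protocol 11.4.2. All of this stands. An omission here is an omission from one descriptive table, and the point reaches only events that nobody reports.

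A reader might infer that children are judged against Day 1 for seven years. The SAP does not support that: it ends at Week 145, and switch patients are re-baselined before the extension. For the child entering at 20 months, the wider gap of 145 against 120 bpm needs age 6, which comes after the SAP's horizon.

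A reader might also infer that normal growth will be flagged. The documents give limits, not growth curves. The upper systolic limit rises by 108 − 98 = 10 mmHg from infancy to 6 to <12 years, and by 119 − 101 = 18 mmHg from 2 to <6 years to adolescence. Neither reaches the 20 mmHg criterion. The diastolic step from 59 to 72 does exceed its 10 mmHg criterion, but differences between limits do not show how an individual child's pressure moves. The SAP also does not say which age sets the band. Over 25 weeks, growth should matter little.

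Finally, replacing the baseline would exchange one set of misses for another, as shown above. That objection is decisive against replacement, but not against adding a second summary.

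**Conclusion.** The gap is real and modest in scope. All vital-sign change is taken from one pre-treatment value (the pre-extension value for switch patients), and no planned analysis uses the same infusion's pre-infusion reading. It follows from the Appendix B rules that a within-infusion excursion can be absent from the PCSA table and that a value already present can appear in it. This needs neither growth nor long follow-up: it applies within the 25-week primary period and over the SAP's 145 weeks.

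The size in any one child depends on how far the fixed value lies from the day's value. In the assumed cases, a 45 bpm rise and a 32 mmHg fall go unflagged. How often this would happen cannot be estimated from the documents. The conclusion concerns heart rate and blood pressure only, and a rise that stays below the age limit is flagged under neither approach.

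The missing respiratory-rate criterion is a separate, plain mismatch between Protocol 11.4.2.3 and Appendix B. That section does not name oxygen saturation or temperature, so their absence does not contradict it.

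**What to change.** - **SAP 2.4.4.4:** keep the fixed-baseline PCSA table. Add a summary of the worst during- or post-infusion value against the same infusion's pre-infusion value, for heart rate, systolic and diastolic pressure. Apply the Appendix B limits and change criteria, with the age band set by age at the assessment.
- **SAP 2.1.1:** in the vital-signs sentence, say that the extension re-baselining applies to switch patients.
- **Appendix B:** add a respiratory-rate PCSA criterion to match Protocol 11.4.2.3. Criteria for oxygen saturation and temperature are optional.

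The cost is one extra table, some programming and a short SAP edit. The readings are already collected, and the retained table keeps comparability with other tables that use a fixed baseline. Because the protocol's baseline rule stays in place, the added summary does not depart from it.

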2.1.2 Prior or concomitant medications

Medications and therapies taken by the patient during the 30-day period prior to the Screening/Baseline evaluation visit and during the course of the study will be recorded in the electronic Case Report Forms (e-CRF).

All medications will be coded using the World Health Organization-Drug Dictionary (WHO-DD) using the version in effect at Sanofi at the time of DBL.

- Prior medications are those that are taken in the 30 days prior to first IMP intake as well as pre-study alglucosidase alfa medication for at least the 6 months prior to first IMP intake. Prior medications can be discontinued before first administration or can be ongoing during treatment phase.
- Concomitant medications are any treatments received by the patient concomitantly to the IMP, from first study treatment to the end of treatment + 28 days. A given medication can be classified both as a prior medication and as a concomitant medication. Concomitant medications do not include medications started during the post-treatment period (as defined in the observation period in [Section 2.1.3](#)).
- Post-treatment medications are those the patient took in the period running from the 28 days after last IMP intake up to the end of the study.

